#### 7.5.2.4 $\beta$ -cell Function ( $\beta$ Score)

The components of the  $\beta$  score and the total  $\beta$  score will be summarized descriptively at Day 75  $\pm$  14 days and Day 365  $\pm$  14 days after IAT. The Mann-Whitney U test will be used at each day (Days 75 and 365) in order to compare the distributions of the total  $\beta$  score of the two treatment groups. Testing will be two-sided at the 0.05 level of significance.

#### 7.5.2.5 Proportion of Patients With HbA1c $\leq$ 6.5% at Day 365

HbA1c for Day 365  $\pm$  14 days after IAT will be recorded on CRF Page 24.1 and this value will be used for summarization and analysis. The number and percentage of patients with HbA1c  $\leq$ 6.5% at Day 365  $\pm$  14 days after IAT, the 95% confidence interval for the proportion, the treatment effect (reparixin percentage minus placebo percentage), and the 95% confidence interval for the treatment effect will be presented by treatment group. The percentage of patients with HbA1c  $\leq$ 6.5% at Day 365  $\pm$  14 days after IAT will be compared between treatment groups using the Pearson chi-squared test (two-sided testing at the 0.05 level of significance). If assumptions regarding expected cell counts are not met, Yate's correction will be applied.

#### 7.5.2.6 Cumulative Number of Severe Hypoglycemic Events From Day 75 to Day 365 After IAT

The cumulative number of severe hypoglycemic events from the Day 75 to Day 365 visits (as recorded on CRF Page 24.1) will be summarized descriptively by treatment group.

The effect of treatment on the rate of recurrent episodes of severe hypoglycaemia will be evaluated using an Andersen-Gill analysis with robust sandwich-type variance estimate. From the model, the estimated hazard ratio (reparixin versus placebo), associated 95% confidence interval, and a two-sided p-value assessing the significance of the hazard ratio (at the 5% level) will be presented.

#### 7.5.2.7 Proportion of Patients With HbA1c $\leq$ 6.5% at Day 365 and Free of Severe Hypoglycemic Events From Day 75 Through Day 365

HbA1c for Day 365  $\pm$  14 days after IAT and the number of severe hypoglycemic events from Day 75 through Day 365 will be recorded on CRF Page 24.1, and these values will be used for summarization and analysis. The number and percentage of patients with HbA1c  $\leq$ 6.5% at Day 365  $\pm$  14 days after IAT and who are free of severe hypoglycemic events from Day 75  $\pm$  14 days to Day 365  $\pm$  14 days after IAT, the 95% confidence interval for the proportion, the treatment effect (reparixin percentage minus placebo percentage), and the 95% confidence interval for the treatment effect will be presented by treatment group. The percentage of patients with HbA1c  $\leq$ 6.5% at Day 365  $\pm$  14 days after IAT and who are free of severe hypoglycemic events from Day 75  $\pm$  14 days to Day 365  $\pm$  14 days after IAT will be compared between treatment groups using the Pearson chi-squared test (two-sided testing at the 0.05 level of significance). If assumptions regarding expected cell counts are not met, Yate's correction will be applied.

## 7.6 Safety Analyses

The safety population will be used for the summarization and analysis of all safety data.

### 7.6.1 Adverse Events

All reported verbatim adverse event terms will be mapped to standard system organ classes and preferred terms using the MedDRA Dictionary as specified in the Data Management Plan for this protocol.

REP0112

Statistical Analysis Plan

A treatment emergent adverse event (TEAE) is defined as any recorded adverse event which started on or after Day 1 of investigational product administration. If the start date of an adverse event is incomplete or missing, the event will be assumed to be a TEAE, unless the incomplete start date (month and/or year) or the stop date (complete or incomplete) clearly indicates that the event started prior to dosing.

The relationship of each adverse event to investigational product will be recorded as none, unlikely, possible, probable, or highly probable. If a relation is missing for an adverse event, the relation of the event to investigational product will conservatively be assumed to be highly probable for summarization.

The severity of each adverse event will be classified as mild, moderate, or severe. If the severity of an adverse event is missing, the severity of the event will conservatively be assumed to be severe for summarization.

Serious adverse events will be those events indicated as such on the CRF (a "Yes" response to "Serious").

An overview of TEAEs will summarize the number and percentage of patients and the number of events in the following categories: any TEAE, any TEAE by relationship to investigational product, any TEAE by severity, any serious TEAE, any serious TEAE by relationship to investigational product, any serious TEAE by severity, any TEAE resulting in early withdrawal from study, and death. For this overview, patients and events will be counted at each level of relationship to investigational product or severity at which an event is experienced (and not by worst relationship to investigational product and maximum severity).

The number and percentage of patients reporting at least one event and the number of events reported within system organ class and preferred term will be summarized by treatment group and in total for the following type of adverse events: TEAEs, TEAEs leading to discontinuation of the investigational product, TEAEs leading to early withdrawal from the study, serious TEAEs, serious TEAEs leading to discontinuation of the investigational product, and serious TEAEs leading to early withdrawal from the study. Patients will be counted only once within each system organ class and preferred term for which they experience at least one event.

A similar tabulation of these data, broken down further by relationship to investigational product, will be presented for TEAEs and serious TEAEs. Patients with multiple events within a particular system organ class or preferred term will be counted only under the category of their most related event within that system organ class or preferred term. Each category of relationship will be presented on a separate page or pages.

A similar tabulation of these data, broken down further by severity, will also be presented for TEAEs and serious TEAEs. Patients with multiple events within a particular system organ class or preferred term will be counted only under the category of their most severe event within that system organ class or preferred term. Each category of severity will be presented on a separate page or pages.

Listings will be presented by patient within treatment group for all adverse events, serious adverse events, adverse events leading to early withdrawal from the study, adverse events resulting in discontinuation of investigational product, and deaths.

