## **12.5. DATA MONITORING COMMITTEE**

An independent Data Monitoring Committee (DMC) will be established and will be responsible for safeguarding the interests of trial participants, and for enhancing the integrity and credibility of the trial. The DMC will assess the safety and efficacy of the interventions during the trial, and will monitor the overall conduct of the clinical trial. The DMC will provide recommendations to Dompé about stopping or continuing the trial. To contribute to enhancing the integrity of the trial, the DMC may also formulate recommendations to Dompé relating to the selection/recruitment/retention of participants, their management, improving adherence to protocol-specified regimens and retention of participants, and the procedures for data management and quality control.

The DMC will operate independently of Dompé, and its members will not have connections to Dompé with the exception of the compensation to DMC members related to their activities.

The DMC will comprise three members. They will be a multidisciplinary group that will include:

- Two surgeons/physicians with extensive experience in islet transplantation and critical care medicine (e.g. a Medical Director of a Transplant Program);
- A Biostatistician with substantial experience in the DMC process.

The DMC:

- Will review unblinded data. To this purpose, an Independent Statistician will liaise with the CRO statistician and will have access to those components of the database necessary to generate the reports to the DMC.
- Will be responsible for the ongoing (at least every 4 months) review of safety data throughout the trial. Primary among the safety data that will be reviewed are Serious AEs. In particular, the DMC will monitor the number of deaths for both arms of the study to assess whether mortality is consistent with historical data. The DMC also will give attention to post-surgical reoperation and clinically significant coagulation abnormalities (intra-abdominal as well as gastrointestinal hemorrhage have been reported to be the most common reasons for reoperation).
- Will review efficacy data in an ongoing manner to enable the assessment of the acceptability of safety in the context of emerging evidence about efficacy, i.e. measures of metabolic control and graft function.

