## 14. APPENDICES

### 14.1. APPENDIX 1 – CUMULATIVE SUMMARY OF ADVERSE DRUG REACTIONS

MedDRA Body System / LLT	Non Serious	Serious	Frequency
Blood and lymphatic system disorders	3	1	4.30%
Anaemia	2		
Coagulopathy		1	
Lymphadenopathy	1		
Cardiac Disorders	1	0	1.08%
Tachycardia	1		
Gastrointestinal Disorders	13	0	13.98%
Abdominal pain NOS	1		
Dyspepsia	1		
Flatulence	2		
Gastroesophageal reflux disease	1		
Nausea	6		
Vomiting	2		
General disorders and administration site conditions	21	0	22.58%
Canula site reaction	13		
Fatigue	1		
Injection site thrombosis	3		
Infusion site oedema	2		
Lethargy	1		
Oedema peripheral	1		
Immune system disorders	0	1	1.08%
Lung transplant rejection		1	
Injury, poisoning and procedural complications	1	0	1.08%
Complications of transplanted kidney	1		
Investigations	2	0	2.15%
Blood amylase increased	1		
Liver function test abnormal	1		
Metabolic and nutrition disorders	1	0	1.08%
Hyperkalaemia	1		
Musculoskeletal and connective tissue disorders	1	0	1.08%
Arthralgia	1		
Nervous system disorders	25	0	26.88%
Dizziness	3		
Headache	8		
Hypoesthesia	3		
Somnolence	11		
Psychiatric disorders	4	0	4.30%

Adverse Drug Reactions - Number of Reports by Terms			Frequency
MedDRA Body System / LLT	Non Serious	Serious	
Abnormal dream	1		
Restlessness	1		
Euphoric mood	2		
Renal and urinary disorders	4	0	4.30%
Renal failure	1		
Renal tubular necrosis	2		
Urinary retention	1		
Respiratory, thoracic and mediastinal disorders	6	1	7.53%
Bradypnoea	1		
Cough	2		
Nasopharyngitis	2		
Respiratory failure		1	
Sore throat	1		
Skin and subcutaneous system disorders	4	0	4.30%
Erythema	1		
Infusion site erythema	2		
Pruritis	1		
Vascular disorders	1	3	4.30%
Haemorrhage		1	
Hypotension	1		
Retroperitoneal haemorrhage		2	
TOTAL	87	6	

1 = table does not include ADRs reported from the ongoing pilot trial in islet allo-transplant patients

The most frequent (>10%) ADRs observed in the phase 1 and phase 2 studies were:

Nervous system disorders (about 27%), including headache, dizziness, hypoaesthesia, somnolence.

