- Will be advisory to Dompé and make recommendations to Dompé regarding the continuation of the trial and potential modifications to the design and conduct of the trial. These recommendations will be made in a manner to maintain confidentiality of emerging information about efficacy and safety, unless access to certain data is needed to enable Dompé to make decisions about the DMC recommendations. Dompé will be responsible for promptly reviewing the DMC recommendations, to decide whether to continue or terminate the trial, and to determine whether amendments to the protocol or changes in the study conduct are required

The independent statistician will use this SAP as a guideline for developing the outputs that are to be produced to facilitate DMC data review and deliberations.

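### No planned safety table gives, by arm, the number of patients with any bleeding event or the number reoperated, although both documents single out these harms

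*SAP*

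**What the plan says.** SAP 7.6.1 plans an overview of treatment-emergent events: any, serious, by relationship, by severity, and "any TEAE resulting in early withdrawal from study, and death". It then plans tables in which "the number of events reported within system organ class and preferred term will be summarized by treatment group and in total", with further versions by relationship, by severity, and for events leading to discontinuation or withdrawal. The counting rule is: "Patients will be counted only once within each system organ class and preferred term for which they experience at least one event". By-patient listings within treatment group are planned for all adverse events, serious events, events stopping the product, events leading to withdrawal, and deaths.

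SAP 7.6.2 adds by-arm summaries of coagulation tests: aPTT and INR out of range at screening and discharge, and INR, PTT and fibrin degradation products on Days 1 to 7.

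Protocol 12.5 says: "The DMC also will give attention to post-surgical reoperation and clinically significant coagulation abnormalities". SAP 8 repeats this. Protocol 9.4.5 and SAP 9 state that early termination would be considered if complications requiring reoperation reliably exceed the rate expected in standard practice. They name intra-abdominal and gastrointestinal haemorrhage as the commonest reasons for reoperation. SAP 8 ends: "The independent statistician will use this SAP as a guideline for developing the outputs that are to be produced to facilitate DMC data review".

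**The concern.** The documents name the harm that matters most to the DMC, but the table list does not summarise it. Bleeding events may fall in more than one organ class. Reoperation is something done about an event, so it has no row of its own unless a site happens to enter it as an event term, and even then no table isolates it. A reader of the study report would have to assemble both counts from listings, with the grouping chosen after the treatment codes are known.

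Other safety items are treated more fully. Steatorrhea and malnutrition risk have their own tables with 95% confidence intervals (SAP 7.6.4, 7.6.5). Documented hypoglycemia and ketoacidosis have between-arm tests (SAP 7.6.6, 7.6.7). ALT and AST have a model with adjusted differences (SAP 7.6.2.2). At stake is a pre-specified by-arm estimate of clinical bleeding and of reoperation.

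**Working it through.** **1. Table count.** SAP 10 lists 11 adverse-event tables (14.3.1.1 to 14.3.1.11), 6 laboratory tables (14.3.4.1 to 14.3.4.6) and 7 others (14.3.5 to 14.3.11): 11 + 6 + 7 = 24. Tables with a pooled bleeding count: 0. Tables with a reoperation count: 0. The nearest surgical output is Listing 16.2.4.7, a patient listing. The contents list of the SAP addendum shows no safety section.

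**2. Appendix 1 reproduced.** The table is headed "Adverse Drug Reactions - Number of Reports by Terms". Total reports: 87 non-serious + 6 serious = 93. Vascular disorders: (1 + 3)/93 = 4.30%, as stated, so the frequencies are shares of reports, not of patients.

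The six serious reports:

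| Term | Organ class | Serious reports |
|---|---|---|
| Haemorrhage | Vascular | 1 |
| "Retroperitoneal haemorrhage" | Vascular | 2 |
| "Coagulopathy" | Blood and lymphatic | 1 |
| Lung transplant rejection | Immune system | 1 |
| Respiratory failure | Respiratory | 1 |

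Haemorrhage is 3/6 = 50%. With coagulopathy it is 4/6 = 67%, in two organ classes. All three haemorrhage reports share one class. That class also holds a hypotension report, so its row is not a pure bleeding count.

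**3. Why rows do not give the patient total.** Patients are counted once per class and once per term, and one patient can appear in several rows. Suppose three bleeding rows in different classes show 3, 2 and 1 patients. The number of distinct patients is then anything from 3 (full overlap) to 3 + 2 + 1 = 6 (none).

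**4. What an estimate would show (assumed counts).** With 100 patients randomized 1:1, take 50 per arm.
- Pooled, 10/50 versus 2/50: difference 0.20 − 0.04 = 0.16. SE = √(0.20×0.80/50 + 0.04×0.96/50) = 0.063. The 95% CI is 0.16 ± 1.96 × 0.063, or 3.7 to 28.3 points. Fisher p = 0.028.
- One row, 3/50 versus 1/50: Fisher p = 0.62.

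**5. Sensitivity to splitting (assumed rates).** I enumerated two binomials with n = 50 per arm. The criterion was z = (p̂₁ − p̂₀)/√(2p̄(1 − p̄)/50) > 1.96.

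| Assumed rates | Pooled | Per row, 3 rows | Per row, 4 rows | Per row, 5 rows |
|---|---|---|---|---|
| 20% vs 6% | 0.584 | 0.177 | 0.117 | 0.077 |
| 24% vs 8% | 0.623 | 0.196 | 0.141 | 0.101 |
| 30% vs 10% | 0.734 | 0.247 | 0.183 | 0.141 |

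The per-row figures assume an even split and overstate the loss, for three reasons:
- At 24% vs 8% over four rows treated as independent, the chance that at least one row shows the excess is 1 − (1 − 0.141)⁴ ≈ 46%.
- If 75% of events fall in one class (18% vs 6%), that row alone has about 48%.
- For a mere doubling, 12% vs 6%, even the pooled count reaches only about 17%.

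**The case against.** Much of the information is already in the planned outputs. By-patient listings within treatment group let anyone pool recorded bleeds. A reoperation that prolongs the stay or needs readmission makes its event serious under Protocol 8.1.2, so the event enters the by-arm serious tables, though not labelled as reoperation. Class rows pool within a class, and in Appendix 1 every haemorrhage report sits in one class. The DMC sees unblinded data under a Charter that is not among these documents, and the SAP is only a guideline for its outputs. All of this stands. It rules out several stronger readings that a reader might infer:

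- That a bleeding excess would pass unseen. The listings and the DMC's review could reveal it.
- That bleeding would certainly be scattered over many small rows. The documents show a second class only for one coagulopathy report. Coding of gastrointestinal bleeds to a third class is an assumption.
- That the DMC would have no look at reoperation by arm. The Charter or the independent statistician may provide one.
- That bleeding is an established harm of the drug. Appendix 1 rests on six serious reports with no placebo column, and Protocol 2.4.3 describes the phase 2 adverse-event profile as similar in the two groups.

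The objection does not supply a pre-specified count with an estimate. Listings are not a summary, and grouping terms after unblinding invites dispute. Laboratory coagulation values are not clinical bleeds. Abnormal PTT and INR during prophylactic anticoagulation are also exempt from adverse-event recording (Protocol 8.5).

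**Conclusion.** The gap is real and modest. No planned table counts, by arm, patients with any bleeding event or patients reoperated, although the documents single out both. This follows from SAP 7.6.1 and SAP 10 alone and needs no assumption about rates.

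Its size cannot be derived from the documents, which give no bleeding or reoperation rate for this population. The figures above only illustrate that a pooled patient count is easier to read than its parts. Comparing 62% pooled with 14% per row should not be read as the power lost: the rates and even split are assumed, about 46% is the fairer four-row figure under independence, and SAP 7.6.1 plans no test of adverse events. The change is a worthwhile, inexpensive improvement to the safety reporting. It does not question the primary analysis.

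**What to change.** Add one paragraph to SAP 7.6.1 and one table to SAP 10, by treatment actually received, in treated patients. State that this is the dosed subset of the SAP safety population, which is all randomized patients. Report the number of patients with:

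- (a) at least one haemorrhage adverse event, pooled across organ classes from a term list fixed before unblinding, with clinical coagulopathy events on a separate line because of the recording exemption in Protocol 8.5;
- (b) the same for serious events;
- (c) at least one reoperation, overall and for bleeding, identified from recorded action-taken and SAE data.

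For each, give n, %, the reparixin-minus-placebo risk difference and an exact or score 95% CI. Include the table in the DMC outputs. A footnote should say that after discharge only SAEs and relevant untoward events are recorded (Protocol 8.3.1), so non-serious bleeds come mainly from the hospital stay.

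The cost is a short SAP addition, one table, and a blinded review before database lock to settle the term list and identify reoperations. How easy that review is depends on the CRF fields, which the documents do not show. Protocol 8.3 requires treatments given or other action taken to be recorded, so no new visits or patients are needed.

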## 7.6.2 Laboratory Data

### 7.6.2.1 Safety Laboratory Parameters

Safety laboratory parameters to be summarized include the following.

- Hematology: hematocrit, hemoglobin, platelets, red blood cells, white blood cells, and differential white blood cells count (neutrophils, lymphocytes, monocytes, eosinophils, basophils).

REP0112

Statistical Analysis Plan

- Clinical chemistry: sodium, potassium, blood urea nitrogen, serum creatinine, total bilirubin, ALT, AST.
- Coagulation: activated partial thromboplastin time (aPTT) and international normalized ratio (INR).

Samples for safety laboratory parameters are taken at screening and hospital discharge. Each parameter will be summarized as the number and percentage of patients at each visit with out-of-range results and with out-of-range clinically significant (as reported by the investigator on the laboratory CRFs) results by treatment group and in total.

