#### **9.4. STATISTICAL METHODOLOGY**

All patient data collected on the CRF and on the Diary will be listed by patient, treatment group and centre.

Appropriate descriptive statistics will be produced, according to the variable. For continuous variables, the data will be presented according to a clinically relevant discretization. For categorical data, frequencies and percentages will be presented. If appropriate, confidence intervals around the mean or the proportions will be presented.

All the AUC analyses will be based on actual rather than scheduled timings and will be calculated using the trapezoidal rule. If the actual time is not recorded, the scheduled time will be used instead. For ease of interpretation, the AUC value obtained will be divided by the total time the scale is assessed for reporting purposes.

The data will be presented in the Clinical Study Report. A Statistical Analysis Plan will be issued describing details of all the statistical methods and analyses to be applied to trial results, including alpha spending and testing for multiple endpoints. Any deviations from the original statistical plan will be described in the Clinical Study Report.

All reasonable efforts will be made to prevent missing data. Thoughtful methods for imputation of missing data will be presented in the Statistical Analysis Plan for the clinical trial

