#### 9.4.3. Safety analysis

Safety variables will be presented for the Safety population, by treatment group.

All AEs will be coded using the most up-to-date version at the time of database lock of the MedDRA and will be presented by primary system organ class and preferred term. AEs will be presented in terms of the incidence, severity and relationship to the study drug, overall and by body system and preferred term. SAEs will be presented in the same way.

Results for laboratory test at screening and hospital discharge will be assessed as being within the normal range or outside the normal range and clinically-significant outside results. The following parameters will be also presented at different time points: AST/ALT, INR/PTT, fibrin degradation products (XDPs), C-reactive protein (CRP) will be presented for all daily from day 1 up to day 7 after transplant and on day  $75 \pm 5$  after transplant for AST/ALT. Serum level of albumin and pre-albumin will be summarized as absolute values and change from pre-transplant value at day  $75 \pm 14$  and  $365 \pm 14$  after transplant.

Vital signs at each time point and the change in vital signs from pre-transplant value, and weight loss will be presented using descriptive statistics.

Steatorrhea and malnutrition risk will be graded as described in 4.2.3. Analysis will be performed separately at day  $75 \pm 14$  and  $365 \pm 14$  after transplant. 2x4 contingency table will be performed at each time point. 95% confidence intervals of proportion will be also done.

Analysis of documented hypoglycemia episodes and diabetic ketoacidosis-related events, recorded as cumulative number of episodes per patient, will be performed from day  $75 \pm 14$  to  $365 \pm 14$  after islet infusion. Mean, median, SD, min, max will be calculated for the interval

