## 7 STATISTICAL METHODS

### 7.1 General Principles

The statistical package SAS® will be used to produce all summary tables, figures, and listings.

In general, categorical data will be presented using counts and percentages, whilst continuous variables will be presented using the number of patients, mean, standard deviation, median, minimum, and maximum. Denominators for calculation of percentages will be taken as the number of non-missing responses in the specified analysis population and treatment group unless otherwise stated, and percentages will be rounded to one decimal. Minima and maxima will usually be reported to the same level of accuracy as the raw data; means, medians and standard deviations will be presented to one further decimal place; standard errors (if presented) will be presented to 2 decimal places more than the raw data.

REP0112

Statistical Analysis Plan

All data recorded in the CRF will be listed.

Unless otherwise specified, the significance level used for statistical testing will be 5% and two-sided tests will be used.

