#### 7.6.2.2 Post-transplant Safety Laboratory Parameters

Post-transplant safety laboratory parameters to be summarized include the following.

- AST, ALT, INR, PTT, fibrin degradation products, and C-reactive protein.

Samples for post-transplant safety laboratory parameters are taken at Days 1 through 7 post-transplant and on Day 75 ± 14 days for AST and ALT. Each parameter will be summarized descriptively at each applicable time point by treatment group and in total.

Change from baseline (screening) at each applicable follow-up time point will be summarized for AST and ALT by treatment group and in total. Change from baseline (screening) will be analyzed within a single repeated measurements model (for each of AST and ALT) using PROC MIXED within SAS®. The model will include fixed effect terms for site, time (Days 1 through 7 and 75), and treatment; the treatment by time interaction; the treatment by study site interaction if significant at the 0.10  $\alpha$ -level; baseline value as a covariate; and a random effect for patient. A compound symmetry covariance structure will be used to account for the multiple observations from the same patient.

The adjusted least squares means and associated 95% confidence intervals will be estimated for each combination of day and treatment, and the adjusted least squares mean difference (reparixin minus placebo) and associated 95% confidence interval at each day will also be estimated. The treatment effect within each day will be tested using a two-sided test at the 5% level. The tests of the fixed effects in the model will also be presented.

Observed values for all parameters will also be presented as box plots for each treatment group at each time point.

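### Screening and discharge safety laboratory tests are tabulated only as two counts, with no values, no change from screening and no stated direction, so a moderate between-arm shift could be missed

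*SAP*

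**What the plan says.** SAP 7.6.2.1 covers the haematology panel with differential, the chemistry panel including creatinine and bilirubin, and aPTT and INR. "Samples for safety laboratory parameters are taken at screening and hospital discharge". The planned output has two tiers. The first is: "Each parameter will be summarized as the number and percentage of patients at each visit with out-of-range results". The second is the same count restricted to results flagged as clinically significant by the investigator on the laboratory CRF pages. Both are shown by treatment group and in total, in Tables 14.3.4.1 to 14.3.4.3.

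Protocol 9.4.3 sets the same rule: results "will be assessed as being within the normal range or outside the normal range and clinically-significant outside results". Protocol 9.4 states the general approach behind it: "For continuous variables, the data will be presented according to a clinically relevant discretization".

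The SAP's own default differs. Section 7.1 says that in general "continuous variables will be presented using the number of patients, mean, standard deviation, median, minimum, and maximum". For the post-transplant tests (AST, ALT, INR, PTT, fibrin degradation products, CRP), section 7.6.2.2 says: "Each parameter will be summarized descriptively at each applicable time point by treatment group and in total". Section 7.6.2.3 gives albumin and pre-albumin descriptive statistics and change from the pre-transplant value.

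**The concern.** Haematology and most of the chemistry panel are reduced to counts, while comparable continuous tests in the same SAP keep their values. No reason is given. Two kinds of information are lost. A count does not say how far outside the range a result lies. A count with no stated direction also lets a fall in high values offset a rise in low ones.

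The affected tests bear on the protocol's own safety questions:

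- **Bleeding.** Appendix 1 lists 6 serious adverse drug reactions. Four are coagulopathy (1), haemorrhage (1) and retroperitoneal haemorrhage (2). SAP section 9 tells the DMC to pay particular attention to haemorrhage.
- **Kidney.** Appendix 1 also lists renal failure (1) and tubular necrosis (2), and Protocol 6.3.2 says that a major metabolite accumulates when renal function is impaired. Daily renal function appears only as Listing 16.2.8.4.
- **White cells.** Protocol 2.4.2 reports a smaller neutrophil rise on reparixin after cardiopulmonary bypass. A count without direction cannot separate a smaller rise from an abnormally low value.

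**Working it through.** The documents give no figure to reproduce and plan no between-arm test for these parameters. Power is used below only as a measure of how much information each summary keeps.

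**1. Which tests keep their values**

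| Tests | By-arm summary of values |
|---|---|
| AST, ALT, INR, PTT, fibrin degradation products, CRP | Yes, Days 1-7 (7.6.2.2) |
| Albumin, pre-albumin | Yes, with change (7.6.2.3) |
| Haemoglobin, haematocrit, red cells, platelets, white cells and differential, sodium, potassium, urea nitrogen, creatinine, bilirubin | None; two counts only (7.6.2.1) |

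**2. Loss from counting when all abnormalities lie in one direction**

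Inputs from the documents: 100 patients (SAP 3.1), 1:1 (SAP 3.4), so n = 50 per arm; two-sided 5% (SAP 7.1), z = 1.96. Assumed: normal values, downward shift d = 0.67 SD, and placebo out-of-range rate p0.

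- Means: power = Φ(d√(n/2) − 1.96) = Φ(0.67 × 5 − 1.96) = Φ(1.39) = 92%.
- Proportions: p1 = Φ(Φ⁻¹(p0) + d). With p̄ the average of p0 and p1, power = Φ{[(p1 − p0)√n − 1.96√(2p̄(1 − p̄))] / √(p0(1 − p0) + p1(1 − p1))}.
- Example, p0 = 0.90: p1 = Φ(1.282 + 0.67) = 0.975. Power = Φ[(0.527 − 0.672)/0.339] = Φ(−0.43) = 33%.

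| Placebo out of range | Reparixin out of range | Power, proportion | Power, means |
|---|---|---|---|
| 50% | 74.9% | 74% | 92% |
| 70% | 88.4% | 62% | 92% |
| 80% | 93.5% | 51% | 92% |
| 90% | 97.5% | 33% | 92% |
| 95% | 99.0% | 21% | 92% |
| 98% | 99.7% | 12% | 92% |

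For other shifts, at placebo rates of 50%, 90% and 98%: a 0.5 SD shift gives 50%, 23% and 10% (means 71%), and a 1.0 SD shift gives 96%, 49% and 15% (means above 99%). The normal approximation is rough in the rows nearest 100%.

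**3. Loss from merging high and low**

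Assume placebo has 10% low and 40% high, with the same 0.67 SD fall.

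- Low: Φ(−1.282 + 0.67) = Φ(−0.612) = 27%.
- High: 1 − Φ(0.253 + 0.67) = 1 − Φ(0.923) = 18%.
- Merged: 50% on placebo against 27% + 18% = 45% on reparixin.

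Power is 7% for the merged rate and 60% for low alone (about 9% and 62% by exact enumeration). This needs no assumption that most patients are abnormal. Other splits at 0.67 SD:

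| Placebo low / high | Merged, placebo to reparixin | Power merged | Power low alone |
|---|---|---|---|
| 5% / 35% | 40% to 31% | 15% | 46% |
| 20% / 20% | 40% to 50% | 16% | 71% |
| 10% / 10% | 20% to 30% | 20% | 60% |

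**4. The clinically significant tier**

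This tier need not be near 100%. If 10% against 30% were flagged, power would be 71%; at 10% against 20% it would be 29%. It keeps some information, but it rests on investigator judgement and has no stated direction.

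**The case against.** A reader might infer that almost every patient is out of range after this operation, so the table sits at its ceiling and a drug effect such as blood loss would be invisible. The documents do not support that reading.

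- **No ceiling is documented.** Neither document gives a discharge out-of-range rate or a discharge haemoglobin. Protocol 7.1.3 leaves splenectomy to centre practice and gives no frequency. Patients with creatinine clearance below 60 mL/min are excluded, and nothing suggests that creatinine is nearly always abnormal at discharge. At a 50% placebo rate the out-of-range proportion still has 74% power.
- **The count is not the only tier.** The clinically significant tier is reported by arm.
- **Bleeding is captured elsewhere.** All in-hospital adverse events are recorded (Protocol 8.3.1), the definition includes abnormal laboratory findings (8.1.1), and the exemptions in 8.5 do not cover haemoglobin or platelets. SAP 7.6.1 tabulates events by arm and severity. INR, PTT and fibrin degradation products are summarised daily, and the DMC sees unblinded data.
- **Range-based reporting can be defended.** Assays are local, reference ranges are site-specific (Protocol 11.4) and discharge timing follows site practice (7.1.5).

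All of this limits the concern but does not remove it. Adverse event tables capture events that were recognised and recorded, not a moderate shift in values. Listings give no comparison between arms. The DMC's statistician is told to use this SAP as a guideline (SAP section 8), so the same format may reach the DMC. Local ranges are a reason for caution in reading means, not for omitting them. The shells for Tables 14.3.4.1 to 14.3.4.3 are not in the reviewed text and may contain a high/low split, but the governing text does not require one.

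**Conclusion.** The point holds as a gap in safety reporting. It does not affect the efficacy analyses. The SAP and protocol specify two counts and nothing on values, change or direction for haematology, creatinine and the rest of this panel, so a moderate shift could be missed.

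The loss ranges from modest (92% to 74%) to severe (92% to 12%) as the assumed placebo out-of-range rate rises from 50% to 98%. Where abnormalities occur in both directions, merging them can nearly cancel a real shift. These results rest on normal distributions, an assumed 0.67 SD shift and assumed placebo rates; the documents supply only the 50 per arm and the 5% level. They describe the first tier. How much the clinically significant tier recovers depends on how investigators apply it.

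**What to change.** In SAP 7.6.2.1 and Tables 14.3.4.1 to 14.3.4.3, keep the two existing counts and add, by arm:

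- descriptive statistics for observed values at screening and discharge, in the SAP 7.1 format, and for change from screening to discharge;
- low/normal/high shift tables from screening to discharge, using each site's own reference range.

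Add a note that assays are local and that discharge day varies by patient and site, so that the means are read with this in mind.

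The cost is a few more table shells and their programming. The values are already collected and appear in Listings 16.2.8.1.1 to 16.2.8.2.11. No new data, visits or hypothesis tests are needed.
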